3.5 Data collection, clinical examinations and evaluation of results

In this project, wearable devices such as the Galaxy Watch will be used. 5 together with Galaxy series smartphones (A or S line) for the acquisition of blood pressure measurements, arterial hemoglobin oxygen saturation (SpO2), heart rate and ECG. This data will be transmitted to a repository, in a secure cloud environment, which meets the requirements of the General Data Protection Act

(LGPD) (Figure 5). In addition, data will be transmitted to a platform to be developed by InCor's IT team, as part of the project, and integrated into InCor's electronic medical record through the WebAdmin tool .

[figure not shown]

Figure 5 . Conceptual diagram for the Telemonitoring Platform.

The division of the study into phases and activities was carried out according to the table and description below.

Phase	Local	Activity
Phase 1	outpatient	
 • Inclusion of patients • Preoperative consultation; • Meeting with the project coordination team; • Complete anamnesis; • Application of the TCLE; • Collection of additional and contact information;
Level 2	hospitalization	
 • Hospitalization; • Eventually, some patients may be included in the study after hospitalization, prior to surgery, with the application of informed consent at this time;
phase 3	surgical	
 • Performing the surgical procedure; • Intraoperative data collection; • Postoperative evaluation and discharge • Patient guidelines; • Signature of the equipment loan liability term (smartphone and smartwatch); and the term for using data from the Electronic Health Record; • Calibration: 
 - BP, serial measurements - smartwatch SAMSUNG + traditional auscultatory method; - ECG - smartwatch SAMSUNG + traditional ECG; - SpO2 - SAMSUNG smartwatch oximetry + traditional oximetry; • Questionnaire of events observed during the remote phase;

Phase 4	remote collection	
 Tracking, monitoring and managing each participant's remote data collection for 30 ± 3 days; these being: 
 - Automatically collected: SpO2, heart rate, steps and sleep. - Collected manually: blood pressure and ECG. Telephone contact, teleconsultations, and unscheduled face-to-face consultations in cases of complications;
Phase 5	outpatient	
 Return outpatient consultation; Meeting with the project coordination team; Return of equipment used in the remote phase; ECG - smartwatch SAMSUNG ; SpO2 - smartwatch SAMSUNG + traditional oximetry; PA - smartwatch SAMSUNG + traditional auscultatory method; Quality of life questionnaire adapted to record the patient's perception during the remote monitoring phase; Issuance of a report confirming or not the classification of the ECG issued by the smartwatch;
phase 6	InCor	
 Description of tests carried out and compilation of final results; Definition, description and justification of the statistical tests chosen and aligned with the hypotheses raised at the beginning of the study.

Table 1: Protocol phases, locations and activities.

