3.8 Traditional electrocardiography (ECG) *versus* SAMSUNG smartwatch ECG

Still in phase 3 of the project, resting electrocardiography (ECG) tests will be performed in conjunction with ECG collection from the *smartwatch SAMSUNG*, for comparison between the two analysis methods (gold standard vs. device).

All electrocardiograms will be performed at a speed of 25mm/ sec, with 1mV/10mm calibration, in a MAC 2000 ECG Machine (GE Medical Systems Information Technologies, Inc., WI, USA) on an outpatient basis. The electrodes will be placed in the classic way of 12 leads (6 in the frontal plane D 1,D 2,D3,aVr,aVl,aVf and 6 in the horizontal plane V1,V2,V3.V4,V5,V6). The parameters will be evaluated by the clinical cardiologist, who will issue a report, based on the guidelines of the Brazilian Society of Cardiology on analysis and issuance of electrocardiographic reports.

3.9 Peripheral oxygen saturation (SpO₂) measurement by SAMSUNG *smartwatch* versus standard oximetry

SpO₂ values will be measured simultaneously by the *smartwatch* **SAMSUNG** and a digital pulse oximetry equipment (G-TECH 302L). Traditional oximetry, using an infrared light beam, simultaneously measures heart rate and peripheral oxygenation in percentages of 0-100%, and measurements above 95% will be considered normal. This evaluation will be carried out in phases 3 and 5 of the project.

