3.10 Blood pressure (BP) measurement by SAMSUNG *smartwatch* versus standard device

smartwatch will first be calibrated **SAMSUNG** for BP measurement following the instructions of the equipment itself. From then on, 8 consecutive measurements will be taken, at rest, alternating between using the *smartwatch* **SAMSUNG** and the arm pressure gauge (Brand *Welch*) standard, which uses aneroid meter and pulse auscultation (stethoscope *littman clinic*). Measurements with the standard device will be performed with the patient in the supine position, after 10 minutes of rest with 3 consecutive measurements. Additionally, a measurement will be performed in a sitting position and another measurement in an orthostatic position with a 30-second difference between measurements.

This assessment will be repeated in phase 5 of the project, following the same methodology described above.

3. 11 Definition of alerts – teleassisted group

The multidisciplinary team will receive alerts through the application platform, according to pre-established limits of blood pressure, heart rate and blood oxygen saturation.

- Blood pressure

Normal Parameters: Systolic [100 – 140 mmHg] and diastolic [70-90 mmHg]

Yellow Alert: Systolic [100 – 180 mmHg] and diastolic [90 – 110 mmHg]

Red Alert: Systolic [<90 and >180 mmHg] and diastolic [<60 mmHg and >100 mmHg].

- Heart Rate:

Normal parameters: HR detection between 60-100 bpm.

Red Alert: Detection of HR < 50 bpm outside sleep period; or HR > 100 bpm (concurrently assessed by watch)

- Oxygen Saturation:

Normal parameters: 95 – 100%

Yellow Alert: 91 – 95%

Red Alert: <90%

The conduct and actions planned to be taken by the clinical team after receiving the alerts through the Si3 platform (on D+1), as well as the guidelines that teleassisted patients will receive at the time of hospital discharge, are described in the table below:

INFORMAÇÕES AO PACIENTE

INFORMAÇÕES À EQUIPE CLÍNICA

[figure not shown]
	SITUAÇÃO	ORIENTAÇÃO	INTERVENÇÃO	AÇÃO
	Detecção de FC < 50 bpm fora do período de sono	Realizar medidas de parâmetros indiretos (ECG, P.A. E SPO ²)	Entrar em contato com a enfermeira da equipe pelo telefone	Analisar os parâmetros clínicos e os sintomas do paciente. Enfermeira aciona teleconsulta com o médico se necessário. Em caso de necessidade, o médico orienta o paciente a procurar o PS do InCor

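### The Phase 5 rhythm report is an unmasked over-read of the watch's own label, and no masking is specified for the Phase 3 ECG or cuff BP readers, so agreement may be overstated

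*Combined protocol and SAP*

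**What the plan says.** All references are to the combined protocol and SAP.

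- **Phase 5 rhythm report (3.5, Table 1).** The return visit includes "Issuance of a report confirming or not the classification of the ECG issued by the smartwatch". In the same row the ECG item is "ECG - smartwatch SAMSUNG" with nothing paired to it, whereas SpO2 and BP are each paired with a traditional method.
- **Phase 3 ECG (the section 3.8 that compares the two ECGs).** A resting 12-lead ECG is recorded together with the watch ECG so that the methods can be compared. "The parameters will be evaluated by the clinical cardiologist, who will issue a report, based on the guidelines of the Brazilian Society of Cardiology". Whether the cardiologist has the watch trace or label is not addressed.
- **Blood pressure (3.10).** The watch "will first be calibrated". After that, "8 consecutive measurements will be taken, at rest, alternating between using the" watch and an arm cuff gauge. The cuff is the "standard, which uses aneroid meter and pulse auscultation". The number of observers, the visibility of the watch display and the order of recording are not given. The assessment is repeated in Phase 5.
- **SpO2 (3.9).** The watch and a digital oximeter are read simultaneously, which leaves little room for observer judgement.
- **Masking.** The only similar wording in the available text is in 3.4, and it concerns randomization, not the reading of reference tests.

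**The concern.** An accuracy study needs a reference reading made independently of the device under test. A reader who knows the device's answer may settle a borderline trace, or a borderline Korotkoff sound, in its favour. Each such reading turns a disagreement into an agreement. Sensitivity, specificity and BP agreement can then all look better than they are.

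The Phase 5 report has this dependence built into its definition. In the Phase 3 ECG and the cuff readings, the protocol leaves room for it. What is at stake is the comparison with reference equipment in 2.2 and 3.6, which is also the reason given in 3.1 for the size of the sample.

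**Working it through.** **Is masking excluded, or only unspecified?**

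| Reading | Reader's access to the watch result | Status |
|---|---|---|
| Phase 5 rhythm report | Needed in order to confirm or reject the label | Unmasked by definition; no paired 12-lead listed |
| Phase 3 12-lead ECG | Not addressed | Unspecified |
| Cuff BP, Phases 3 and 5 | Not addressed | Unspecified; reading depends on the observer |
| SpO2 | Digital display | Little affected |

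**How large could the effect be?** The plan gives no accuracy target or power figure, so there is nothing of its own to reproduce. What follows is an illustration.

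Inputs:
- Sensitivity (Se) 0.93 and specificity (Sp) 0.84, the background figures in the introduction.
- AF share of traces p = 0.20 (assumed).
- Fraction d of discordant reference readings changed to match the watch: 0.25 and 0.50 (assumed).

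True cells as fractions of all traces:
- TP = 0.20 × 0.93 = 0.186
- FN = 0.20 × 0.07 = 0.014
- TN = 0.80 × 0.84 = 0.672
- FP = 0.80 × 0.16 = 0.128
- Agreement = 0.186 + 0.672 = 0.858

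Formulas:
- Apparent Se = (TP + d·FP) / (TP + d·FP + (1 − d)·FN)
- Apparent Sp = (TN + d·FN) / (TN + d·FN + (1 − d)·FP)

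At d = 0.25:
- Se = 0.218 / (0.218 + 0.0105) = 95.4%
- Sp = 0.6755 / (0.6755 + 0.096) = 87.6%

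At d = 0.50:
- Se = 0.250 / (0.250 + 0.007) = 97.3%
- Sp = 0.679 / (0.679 + 0.064) = 91.4%
- Agreement = 0.250 + 0.679 = 92.9%, up from 85.8%

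At d = 0 the true 93% and 84% come back.

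**Other AF shares (apparent Se / Sp, %).** The introduction says about 14% of patients with AF after surgery remain in it for up to two weeks. With postoperative AF in 15% to 60% of patients, that is 0.14 × 0.15 = 2.1% to 0.14 × 0.60 = 8.4% of patients, so a low share is also plausible.

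| AF share | d = 0.25 | d = 0.50 |
|---|---|---|
| 5% | 97.0 / 87.5 | 98.6 / 91.3 |
| 15% | 95.7 / 87.5 | 97.5 / 91.4 |
| 20% | 95.4 / 87.6 | 97.3 / 91.4 |
| 40% | 95.0 / 87.7 | 96.8 / 91.5 |
| 60% | 94.8 / 87.8 | 96.6 / 91.8 |

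**In patients.** With 50 watch patients and one paired reading each, expected discordant readings at a 20% share are 50 × (0.014 + 0.128) = 7.1. Deference of 25% to 50% changes 1.8 to 3.6 of them, so a handful of readings moves the result.

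**A counter-case.** Suppose there is no deference but an independent 5% reference error, with AF in 15% of traces.
- Apparent Se = (0.15 × 0.93 × 0.95 + 0.85 × 0.16 × 0.05) / (0.15 × 0.95 + 0.85 × 0.05) = 0.1393 / 0.185 = 75.3%
- Apparent Sp = (0.85 × 0.84 × 0.95 + 0.15 × 0.07 × 0.05) / (0.85 × 0.95 + 0.15 × 0.05) = 0.6788 / 0.815 = 83.3%

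Deference alone always pushes both figures up. Ordinary reading error pulls them down.

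**The case against.** The strongest reply is that the Phase 5 report is not a reference reading at all. The gold-standard ECG comparison sits in Phase 3, no 12-lead is listed in Phase 5, and nothing says that the report feeds an accuracy estimate. It may simply be a clinical over-read. This stands, and it shapes the fix. But nothing keeps the report out of the accuracy analysis either, and it sits in the same row as the Phase 5 SpO2 and BP comparisons.

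A reader might go further than the documents allow in four ways:

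- **That all reference readings are unmasked.** This is established only for the Phase 5 report. For the Phase 3 ECG and the cuff, the text is silent.
- **That alternating watch and cuff is itself a fault.** It is not, because it pairs readings in time. The gap is the absence of any concealment around an observer-dependent reading. It is also unclear which cuff readings alternate: 3.10 gives eight alternating measurements and, separately, three supine, one sitting and one standing with the standard device.
- **That accuracy is biased upward as a matter of fact.** The deference rate has no basis in the documents, and the counter-case shows that the net direction is not fixed. Sensitivity and specificity are not named as planned estimates, and no size can be put on the BP effect.
- **That nothing could repair it afterwards.** Watch data go to a repository (3.5), and the Visit 1 page of the case report form asks for the ECG tracing to be stored. If Phase 3 tracings are kept too, a masked re-read is possible. An auscultatory reading leaves nothing to re-read.

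**Conclusion.** The point holds in a limited form. The Phase 5 rhythm report is unmasked by definition and has no independent 12-lead beside it. For the Phase 3 12-lead ECG and the cuff BP, masking is unspecified rather than ruled out. If readers defer to the watch, agreement will be overstated.

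The illustrated gain is 2.4 to 4.3 points in sensitivity (95.4 − 93.0; 97.3 − 93.0) and 3.6 to 7.4 points in specificity (87.6 − 84.0; 91.4 − 84.0). It rests on the background 93% and 84%, an assumed 20% AF share, assumed deference of 25% to 50%, and no other reference error. The documents fix none of the last three.

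This is a cheap improvement worth making before enrolment. It is more than missing detail, because following the Phase 5 line as written produces a reading that depends on the watch's label.

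**What to change.** 1. **Phase 3 ECG.** The cardiologist reports the 12-lead ECG without the watch trace or label and locks the rhythm classification in REDCap. Only then is the watch classification shown. ECG accuracy is computed from these two stored fields.
2. **Phase 5 report.** The cardiologist classifies the watch trace with the automatic label hidden and locks that reading before seeing the label. Because no 12-lead is scheduled there, the result is reported as agreement between label and over-read, and is kept out of the accuracy analysis against the gold standard. Counting Phase 5 towards that analysis would require adding a 12-lead ECG at the visit. This fix does not assume one.
3. **Blood pressure (3.10).** Keep the alternation. Hide all watch BP values from the cuff observer until the whole series of cuff values is recorded, then take the watch values from the stored data. Hiding only the next watch value is not enough, since earlier ones would still be known. State which cuff readings form the paired series.

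The cost is protocol wording and an order-of-entry rule in a system already in use. No extra staff or test is needed. The session runs slightly slower, and the accuracy figures may look less favourable.

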3. METHODOLOGY

3.1 Place of study

This project will be carried out entirely on the premises of the Instituto do Coração of the Hospital das Clínicas of the Faculty of Medicine of the University of São Paulo. The sample will consist of 100 outpatients, with heart disease undergoing cardiac surgery, and selected during the pre -surgical consultation. The sample size was proposed by the contractor because it is a pilot study to evaluate the accuracy of the equipment in a sample with POAF.

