3. Training of the patient and/or family member responsible for the use of *smartwatch* and *smartphone* to start post-operative remote monitoring;
4. Upon hospital discharge, the patient will receive guidance for follow-up on the platform with the **Smartwatch SAMSUNG™ Galaxy Watch5** ;
5. Remote patient monitoring with **SAMSUNG™ Galaxy Watch5 Smartwatch** and app for 30 ± 3 days;
6. Monitoring by InCor's multidisciplinary team of the parameters collected using the **Smartwatch SAMSUNG™ Galaxy Watch5** and an application installed on a *smartphone*; identifying risks for early interventions in the face of any relevant intercurrentence;

7. Remote monitoring of the patient by teleconsultation, in case of detection of intercurrents. In cases considered serious by the clinical team, patients will be instructed to seek the InCor PS;
8. Face-to-face return to the outpatient clinic 30 ± 3 days after discharge for evaluation by the clinical team and conclusion of participation in the study.

Figure 4. Proposed flowchart for the project.

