3.6. Validation of the Measurement Model and Data Analysis

The measurement validity of *wearables* will be checked against standard reference methods used at InCor, in order to verify the effectiveness of using *wearables* using parametric or non-parametric statistical tests, depending on the normality distribution pattern of the variables to be studied, considering p values <0.05 statistically significant.

The identification, sociodemographic and clinical data of the patients will be registered in the REDCap program, considered as a tool for managing and storing research data³¹ and analyzed using *Statistical Package for the Social Sciences* (SPSS) version 22.0 for Windows.

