4. ESTIMATED SCHEDULE

ACTIVITIES	1st month	2nd month	3rd-7th month	8th month	9th month	10th-12th month
Clinical PT submission to the Scientific Committee and CAPPesq	x					
Analysis of the Clinical PT by the Research Ethics Committee	x	x				
Device Software Installation and Testing			x			
Execution of the Clinical Protocol (inclusion of patients and remote monitoring)			x			
Compilation and analysis of results				x		
Final report				x	x	
Accountability					x	
Submission of scientific articles						x

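### Table 1 schedules the definition of the statistical tests in Phase 6, after the data are in, and no earlier section fixes the hypotheses, the outcome definition or the tests

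*Combined protocol and SAP*

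**What the plan says.** Section 3.5, Table 1, gives Phase 6 two activities. One is "Description of tests carried out and compilation of final results"; the other is "Definition, description and justification of the statistical tests chosen and aligned with the hypotheses raised at the beginning of the study". Phase 6 is the last phase. It comes after the Phase 5 visit, which section 3.4 describes as "Face-to-face return to the outpatient clinic 30 ± 3 days after discharge" and which ends participation.

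The schedule in section 4 agrees: the clinical protocol runs in months 3-7, and "Compilation and analysis of results" falls in month 8.

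The only earlier statistical text is section 3.6, written for validation of the wearable. It provides for "parametric or non-parametric statistical tests, depending on the normality distribution pattern of the variables to be studied", "considering p values <0.05 statistically significant". It names no test, no normality criterion and no estimate. Section 3.4 gives the comparison between arms as a re-hospitalization rate, watch against institutional standard, and names no test for it. Section 2 lists objectives. No hypothesis appears in the available text.

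**The concern.** The Phase 6 line sets a time for choosing the tests, so it is more than a missing detail. On its plain wording, tests are defined when outcomes are already in the database.

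The line ties the tests to hypotheses raised at the start, which would limit the choice if those hypotheses were on record, but none can be found. The outcome wording in section 3.4 is also loose. It links re-hospitalization to scheduled visits and to additional intercurrent events without saying which of these count.

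A reader of the final report could not then tell a planned result from a selected one, either for the arm comparison or for the watch against its reference methods. That cannot be repaired after Phase 6.

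**Working it through.** **Inputs from the protocol.** The threshold is 0.05 (section 3.6; sidedness is not given, so two-sided is assumed). Section 3.6 states it for device validation, so applying it to the arm comparison is also an assumption. There are 100 patients, 50 per arm (sections 3.1 and 3.4). The protocol gives no power, effect size, standard deviation or event rate, so there is no sample-size figure to reproduce.

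**The plan's own figure.** One test fixed in advance rejects a true null with probability 0.05 by definition. Simulation with 50 per arm or 50 pairs and no true difference agrees. The data were assumed normal, exponential or lognormal, with 20,000 two-sample and 5,000 paired replicates:

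- t-test 0.047-0.051; Mann-Whitney 0.048-0.053
- paired t 0.044-0.050; Wilcoxon 0.048-0.053
- t-test or Mann-Whitney chosen by a normality check fixed in advance and applied mechanically (5,000 replicates): 0.047-0.052

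The last line matters. Choosing by normality is not itself the fault; the fault is that the rule is not fixed.

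**Only the test is chosen late.** The rejection rule becomes: smallest p among the candidate tests below 0.05.

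| Candidate tests | Normal | Exponential | Lognormal |
|---|---|---|---|
| t, Mann-Whitney (50 per arm) | 0.061 | 0.069 | 0.077 |
| the same plus t-test on logs | not applied | 0.083 | 0.083 |
| paired t, Wilcoxon (50 pairs) | 0.057 | 0.067 | 0.068 |
| the same plus sign test | 0.067 | 0.078 | 0.079 |

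The result is about 6-8%. For a binary outcome with assumed rates of 10-20%, having both chi-square and Fisher available gives 0.051-0.055, the same as chi-square alone, so late choice between those two adds nothing.

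**The outcome is chosen late as well.** The candidates, which are illustrative, are readmission, emergency visit, unscheduled contact and any contact, each by chi-square, and the contact count by t-test or Mann-Whitney. Assumed rates are 10%, 15% and 25% for the first three, with 50 per arm and no true difference. Each test alone rejects about 5% of the time. The smallest of the six p-values falls below 0.05 in:

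- 15.4% of 4,000 trials in one run with events correlated within patient
- 16-18% as the latent within-patient correlation goes from 0.6 to 0

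At assumed latent correlations of 0.3 and 0.5 the figures are 0.171 and 0.173. Removing Mann-Whitney leaves both unchanged. Choosing only between t-test and Mann-Whitney on the count gives 0.061 and 0.068. Nearly all of the increase above 5% therefore comes from freedom over the outcome.

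As a cross-check by formula, three independent outcomes give 1 − 0.95³ = 0.143, close to the lower end of the range.

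**The case against.** **The Phase 6 line may describe a write-up step.** It speaks of tests already chosen and aligned with earlier hypotheses, and it stands beside a description of tests carried out. This reading is possible. But the line says the tests are to be defined, and no earlier definition exists to be written up. The opening words of section 2.1 and of the outcome sentence in section 3.4 are missing from the available text, so a hypothesis stated there cannot be ruled out.

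**Section 3.6 is a prior rule.** In part it is, for device validation, and a complete rule of that kind would hold the level. As written it names no normality test or cut-off, and it does not cover the arm comparison.

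**The outcome is less open than the simulation assumes.** Section 3.4 sets re-hospitalization apart from the secondary outcomes. This stands, and it is why 15-18% applies only if the definition too is settled late.

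**It is a pilot.** Section 3.1 says "The sample size was proposed by the contractor because it is a pilot study to evaluate the accuracy of the equipment". This lowers the weight of the point. The plan still declares a significance threshold, randomizes 1:1 and expects publication.

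**Two stronger readings are not supported.** A reader might infer that analysts will choose tests with unblinded arm results in view. The protocol does not say so. Its concealment wording attaches to randomization, and the anonymization described before section 4 removes patient identity; arm codes at analysis are not mentioned either way. The watch-versus-reference comparisons have no arm to mask. A reader might also count the multiplicity of the several device comparisons as part of this defect. The same number of tests fixed in advance at 0.05 would carry the same multiplicity, so it has nothing to do with timing and the fix below would not remove it.

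**Conclusion.** The point holds as a should-fix. The documents establish that the only stated time for defining the tests is after follow-up ends, and that nothing in the available text fixes the hypotheses, the outcome definition or the test for re-hospitalization before then.

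The effect on the 0.05 threshold is modest, about 6-8%, if late choice is confined to the test. It is larger, about 15-18%, if the outcome is chosen late too. Both ranges describe an analyst who reports the smallest p-value, so they show what the plan permits and do not predict what will happen. The first depends on the assumed distributions. The second depends on the assumed event rates, the within-patient correlation and the illustrative list of outcomes.

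**What to change.** Move the definition and justification of tests from Phase 6 to months 1-2 of section 4, during ethics submission and review. If enrolment has begun, complete it before any comparative data are viewed. Sign and date a short analysis plan that states:

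- the hypotheses
- what counts as re-hospitalization, and whether unscheduled contacts are part of it
- one estimate and one test or agreement method per objective
- any normality rule in full, with the test and cut-off

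In Table 1, leave Phase 6 with applying and reporting that plan. Label any analysis chosen later as exploratory, without a claim of significance.

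The cost is one line moved, a short document and less freedom to adapt the analysis later. No patients or visits are added, and no delay is expected.
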